7.12 Quality Control

By signing this protocol, all parties agree to following applicable standard operating procedures (SOPs). All parties also agree to ensuring all existing and new study personnel are appropriately trained to ensure the study is conducted and data are generated, documented, and reported in compliance with the protocol, Good Pharmacoepidemiology

PRODUCT: V501/V503	PROTOCOL/AMENDMENT VERSION NO.: V503-088-01-v1
REVOPS ID NO: NIS009722	CORE DRC APPROVAL DATE: 18JUL2024
EPIDEMIOLOGY NO.(PE STUDIES ONLY): EP08039.017	

Practice (GPP), Good Pharmacovigilance Practices (GVP), and all applicable federal, state, and local laws, rules, and regulations. All parties should maintain transparency and open communication in order to effectively manage the study and proactively mitigate any risks.

The Sponsor may conduct routine or for-cause audits to ensure oversight and conduct of the study are completed in accordance with the protocol, quality standards (e.g., GPP and GVP), and applicable laws and regulations. If a significant quality issue (SQI) is identified at any time during the conduct of the study, it must be escalated to the Sponsor immediately. A SQI is any issue with the potential to negatively impact, either directly or indirectly, the rights, safety and well-being of patients or study participants and/or the integrity of the data. In the event an audit or SQI results in corrective or preventive actions, all parties are expected to appropriately implement the action plan in a timely manner.

7.13 Limitations of the Research Methods

This is a register-based study which relies on the use of a proxy codes rather than medical records. It is thus limited in terms of density of data, such that there is not access to all medical details for each case. There is also no available explicit information on lifestyle factors such as smoking and sexual behavior; however, there are several proxy variables that may serve to adjust for potential confounding (Annex 1). However, the bias introduced by these limitations is expected to be minimal for this study, because the Nordic registries have high accuracy, completeness, and in addition high population coverage. Furthermore, these potential limitations are not likely to change, so the results will be comparable throughout the study period. Additionally, with use of registry data from three different countries in the pooled analysis, some variables may need to be adapted to be able to combine information as it is not identical in all registers. Consistent with the related JoRRP study, this will be achieved via development of a common data model, involving collaboration between all Nordic country investigators.

Among the birth cohorts eligible to be vaccinated <17 years of age (i.e., 1990+), herd protection is expected to be greater than among older birth cohorts with lower vaccination coverage. Therefore, it is possible that in the study primary analysis (restricted to 1990+ birth cohorts) vaccine effect estimates may be lower due to lower infection rates among unvaccinated individuals resulting from indirect (herd) protection.

Given that the main cause of RRP globally is infection with HPV type 6 or 11, results are expected to be generalizable. With the proposed study population design, there is restriction in analytical format as having access to the full baseline cohort will yield many technical advantages. The risk for misclassification of exposure to vaccination is minimized through the substantial in-house knowledge of combination of vaccination registries. Nonetheless there is a small but existing risk of non-differential misclassification of outcome. Generalizability is maximized through the population-based sampling frame and allowing all eligible study participants alive and resident in Sweden, Denmark, and Norway at the appropriate time to enter. Also, in recent years, especially the post-vaccination introduction era, Sweden, Denmark, and Norway have experienced high immigration, which may further increase generalizability of study results. The magnitude of random error is minimized in the

PRODUCT: V501/V503	PROTOCOL/AMENDMENT VERSION NO.: V503-088-01-v1
REVOPS ID NO: NIS009722	CORE DRC APPROVAL DATE: 18JUL2024
EPIDEMIOLOGY NO.(PE STUDIES ONLY): EP08039.017	

ecological study through including a very large group of subjects. Yet, it is acknowledged that the rarity of the outcome may lead to some challenges in precision, despite the large baseline study sample size.

7.14 Methods to Minimize Bias

A register-based proxy for definition of outcome (JoRRP and AoRRP) will be used, i.e., ICD-10 code D14.1, which in Sweden is used to register the disease category "benign tumor of the larynx". To increase specificity, the full set of D14.1 cases available will be augmented with appropriate topography/morphology or SNOMED/Norpat codes when available, complete, and recommended by experts. Additionally, in sensitivity analyses, diagnostic and treatment codes described above will be applied to also improve specificity. Given that granulomas of the larynx are largely occurring in middle-age, male smokers, it is suggested that benign tumors of the larynx, other than HPV-associated papilloma, in the specified age ranges (i.e., 0-29 years) and restricted to females, will be very rare. If a misclassification of outcome due to using D14.1 would sometimes occur, it will likely lead to bias towards the null, which means that if vaccine effectiveness against RRP is observed, the true effect is likely greater.

Given the rarity of RRP, and the strong registration of healthcare in the Nordic countries, it is believed that virtually all cases of RRP will be identified by the above algorithm. The risk that a control selected at random from the underlying population is a false negative, i.e., a missed case of RRP, should be negligible.

All immigrant females to Sweden, Denmark and Norway (after age 9) will be excluded to ensure there is no misclassification of exposure, which removes the risk that subjects who have received HPV vaccination outside of these countries are mis-classified as non-vaccinated and ensures a minimum of six years of individual follow-up in the registries prior to case eligibility (at age 15) for exclusion of prevalent RRP cases.

Furthermore, adjustment for potential confounders will be employed in the conditional logistic regression model, for factors that are shown to be associated with both exposure and outcome (see Annex 1 for details). The spectrum of confounding factors can be determined both a priori/empirically, through subject matter knowledge and literature review, but also (once data on potential confounders are collected) by investigation of variables in the regression model, whereby covariates are examined in terms of whether their removal from the model substantially (e.g., by $\geq 10\%$) alters the width of the confidence interval for the observed (odds ratio) association between exposure and outcome in the actual model (nota bene: this is thus not forward selection, which only evaluates association between covariate and outcome and applying a threshold of e.g. p < 0.05 to call a variable a "confounder" – this would not be methodologically correct.)

PRODUCT: V501/V503	PROTOCOL/AMENDMENT VERSION NO.: V503-088-01-v1
REVOPS ID NO: NIS009722	CORE DRC APPROVAL DATE: 18JUL2024
EPIDEMIOLOGY NO.(PE STUDIES ONLY): EP08039.017	

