Gardasil was not available in Sweden, Denmark, and Norway until 2006. Therefore, we plan to capture the cohort of girls/women aged 15 to 29 years beginning 2006 till the most recent registry data are available from each country, which currently is 2021 for Sweden and 2022 for Denmark and Norway. A description and rationale for the age groups, birth cohorts, and calendar years of coverage included for the three participating countries is provided in Table 1 and Figure 1 below.

PRODUCT: V501/V503	PROTOCOL/AMENDMENT VERSION NO.: V503-088-01-v1
REVOPS ID NO: NIS009722	CORE DRC APPROVAL DATE: 18JUL2024
EPIDEMIOLOGY NO.(PE STUDIES ONLY): EP08039.017	

[figure not shown]
Table 1 Description of age groups, birth cohorts, and calendar years of the participants included in the primary and secondary analysis.

Country	Age at diagnosis	Birth cohort	Calendar year – study period
]	Primary analysis (Exposure: HPV vaccination at < 17 years of age)		
Sweden	15 – 29 years	1990 – 2006	2006 through 2021
Denmark	15-29 years	1990 - 2007	2006 through 2022
Norway	15 – 29 years	1990 - 2007	2006 through 2022
Secondary analysis (All available data)			
Sweden	0-29 years	1971 – 2021	2000 through 2021
Denmark	0-29 years	1968 - 2022	1997 through 2022
Norway	0-29 years	1979 - 2022	2008 through 2022

In Figure 1 below, age of participants is represented on the y-axis (horizontal grid lines), calendar year is represented on the x-axis (vertical grid lines), and the birth cohort is represented by the diagonal grid lines and years of birth labelled in the cells. The shaded green areas represent the ages, birth cohorts, and calendar years for the participants included in the study for the primary analysis. Light green shade represents Sweden (with participants followed from the beginning of 2006 through to the end of 2021). Dark green shade represents additional years of coverage for ascertainment of AoRRP outcomes, from the beginning of 2006 through to the end of 2022. Grey shaded areas represent birth cohorts from eligible ages and calendar years of coverage that will not be included in the study as they represent participants who may have received HPV vaccine after 17 years of age. Eligible participants from earlier birth cohorts enter and exit the study period early. For example, a 16-year-old girl born in 1990 will enter the study in 2006 and exit the study in 2019 after reaching the age of 29 years.

PRODUCT: V501/V503	PROTOCOL/AMENDMENT VERSION NO.: V503-088-01-v1

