7.4 Exclusion Criteria

- Subjects who receive a first diagnosis of RRP before age 15 will be excluded for primary analysis, as this more likely reflects a maternally transmitted juvenile-onset case, rather than a sexually transmitted adult-onset case.
- Subjects who immigrated to Sweden or Denmark after 2006, or to Norway after 2008, and age 9 years will be excluded as vaccination exposure status is unknown, and follow-up in registries may be insufficient to determine if incident case is truly new onset (primary objective).
- Subjects who receive the bivalent vaccine Cervarix (recombinant HPV bivalent [types 16 and 18] vaccine, GlaxoSmithKline) will be excluded since it provides no protection against the causative HPV types (6 and 11) in RRP (primary objective).

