The number of possible AoRRP cases (identified using ICD-10 code D14.1) occurring after Gardasil introduction in Sweden, Denmark, and Norway (among females eligible for vaccination before 17 years of age) were estimated by accessing publicly available gross statistics on ICD-10 codes for otorhinolaryngological diseases, and without assessing the proportion of vaccinated individuals among cases and controls, or conducting any preliminary analyses evaluating the association between HPV vaccination and RRP. Initial case counts from Sweden were expected to be between 30 and 60; recent assessment of the total number of cases in the birth cohorts of interest were 46. In Denmark, the estimated number of possible AoRRP cases (identified using ICD-10 code D14.1) occurring after Gardasil introduction was estimated to be between 50 to 90 in eligible birth cohorts. After applying appropriate topography and SNOMED codes to improve specificity, the number of AoRRP cases will be < 50. In Norway, the estimated number of possible AoRRP cases identified in the Norwegian Patient Registry among females ages 15-29 years for the calendar years 2006-2020 (using ICD-10 code D14.1) and birth cohorts of interest (1990+) is between 40 to 70 cases. These numbers will likely be lower after using appropriate topography/morphology (Norpat) codes to improve specificity (also <50).

PRODUCT: V501/V503	PROTOCOL/AMENDMENT VERSION NO.: V503-088-01-v1
REVOPS ID NO: NIS009722	CORE DRC APPROVAL DATE: 18JUL2024
EPIDEMIOLOGY NO.(PE STUDIES ONLY): EP08039.017	

Power calculations:

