There will be no adjustment for multiple comparisons in this study. Analyses have been prespecified, discriminating between primary and sensitivity analyses, and all results will be reported.

Secondary Objective: Calculation of Epidemiological Measure(s) of Interest

Annual age-standardized incidence rates (ASIRs) of JoRRP and AoRRP will be calculated, stratified by age group, gender, and calendar period and the p-values from the test for calendar year trends for these rates will be estimated. New cases of JoRRP or AoRRP will be the numerator for the calculation of incidence rates. The denominator will be the accumulated person-time in each calendar year for which the data are analyzed. As this is a highly robust measure over time and the entire population is sampled, it may not be necessary to include confidence intervals; however, given the small number of cases per calendar year, confidence intervals will be calculated.

Overall incidence rates will be adjusted for age according to European Standard Population, because of the larger proportion of older age groups in Nordic countries compared to the World Standard Population.

Exploratory Objective: Calculation of Epidemiological Measure(s) of Interest (e.g., hazard ratios, incidence rates, test/retest reliability)

Risk factors for AoRRP will be explored in the VE analysis conditional logistic regression model to evaluate if they are independently statistically significantly associated with the outcome of RRP, with all other factors held constant. Specifically, vaccination exposure will be at the reference level, i.e., the analysis of risk factor status will effectively be restricted to non-vaccinated individuals.

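### The six-year registry look-back promised in 7.14 is not delivered by the 7.4 immigrant rule or by the Norwegian data, and the incidence series has no run-in

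*Protocol*

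**What the plan says.** **Immigrants.** Section 7.14 states "All immigrant females to Sweden, Denmark and Norway (after age 9) will be excluded" and sets no calendar limit. It adds that this "ensures a minimum of six years of individual follow-up in the registries prior to case eligibility (at age 15", for the purpose of removing prevalent cases. Section 7.4, which holds the operative criterion, reads "Subjects who immigrated to Sweden or Denmark after 2006, or to Norway after 2008, and age 9 years will be excluded", and marks it as applying to the primary objective.

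**Norwegian data years.** Table 1 in 7.1 heads its lower block "Secondary analysis (All available data" and gives Norway as "2008 through 2022". The upper block gives the Norwegian primary period as "2006 through 2022", for birth cohorts 1990-2007. Section 7.8 counts possible Norwegian cases from the patient registry "among females ages 15-29 years for the calendar years 2006-2020".

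**Incidence series.** Section 7.11 says "New cases of JoRRP or AoRRP will be the numerator for the calculation of incidence rates" and plans a test for calendar-year trend. Section 7.6.2 defines a case by one or more records at first diagnosis. The series run from 2000 in Sweden, 1997 in Denmark and 2008 in Norway. No run-in or washout is stated. Section 5 intends the rates before and after vaccine introduction to give an ecological view of vaccine impact.

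**The concern.** RRP is a recurrent disease. Section 5 reports that nearly a fifth of patients need more than 40 procedures in a lifetime. The first record in a registry is therefore a new diagnosis only if the registry could have seen the patient earlier. The protocol relies on a six-year guarantee for this, and the guarantee depends on an immigrant rule that the exclusion criteria do not contain and on Norwegian records that may not exist.

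Three things are at stake:

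- **Cohort definition.** A programmer working from 7.4 and one working from 7.14 would build different cohorts.
- **Primary analysis.** Excluding women diagnosed before 15 (7.4) needs records from before 15. Where there are none, juvenile-onset or long-standing disease is counted as adult-onset.
- **Secondary analysis.** If old disease is counted as new when a series opens, the early rates are too high and later rates appear to fall. Section 7.13 argues that results stay comparable because the registry limitations do not change over time. Look-back depth does change: it grows with each calendar year.

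**Working it through.** **1. The stated figure.** Age 15 minus age 9 gives 6 years, so the number in 7.14 follows from its own rule. The question is whether it is a minimum for everyone included.

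**2. Immigrants retained under 7.4.** Women who arrived at age 10 or older, up to and including the cut-off year, stay in:

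- Sweden and Denmark, arrival by 2006: cohorts 1990 to 2006 - 10 = 1996.
- Norway, arrival by 2008: cohorts 1990 to 2008 - 10 = 1998.

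A woman born in 1990 who moved to Sweden in 2005 arrives at 15, with 0 years of look-back at that age. A woman born in 1993 who moved to Norway in 2007 arrives at 14, with 1 year. Section 5 dates initial licensure to 2006, so those reaching Norway in 2006-2008 may also have been vaccinated abroad and be recorded as unvaccinated. Section 7.14 says this risk is removed.

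**3. Native-born women.** Registry years before age 15 = (birth year + 15) - first data year, floored at 0.

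- Sweden from 2000: born 1990, 2005 - 2000 = 5 at age 15, and 6 at study entry in 2006; all later cohorts have 6 or more.
- Denmark from 1997: born 1990, 2005 - 1997 = 8; all later cohorts have more.
- Norway from 2008: 0 for births 1990-1993, 1 for 1994, 3 for 1996, 5 for 1998, 6 from 1999. Nine of 18 cohorts fall short, four of them with no look-back.
- Norway from 2006: 0 for 1990-1991, 3 for 1994, 5 for 1996, 6 from 1997. Seven of 18 fall short, two of them with none.

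Counting one unit per cohort and calendar year at ages 15-29 in 2006-2022, and assuming equal cohort sizes, Norway has 164 units. The short cohorts supply 119/164 = 73% of them if data start in 2008, or 98/164 = 60% if they start in 2006.

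**4. Run-in in the incidence series (illustration).** The protocol gives no duration or contact frequency, so these are assumptions: constant true incidence, exponentially distributed active disease with mean T years, and a yearly probability q of a registry contact. At the start, the pool of existing patients equals T years of new cases. The ratio of counted to true new cases in series year k is

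r(k) = 1 + qT[(1 - q)e^(-1/T)]^(k-1).

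For T = 5 and q = 0.6: r(1) = 1 + 3 = 4.0; r(2) = 1 + 3 × 0.4 × 0.819 = 1.98; r(3) = 1.32. Over T = 2, 5, 10 and q = 0.3, 0.6, 0.9, the first-year ratio runs from 1.6 to 10. A straight line fitted to log r(k) gives these false trends per year:

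- Norway 2008-2022: -1.9% to -8.5%; after dropping six years, 0 to -1.9%.
- Sweden 2000-2021: -1.0% to -4.5%; from 2006 onward only, 0 to about -0.9%.
- Denmark 1997-2022: -0.7% to -3.4%; from 2006 onward only, 0 to -0.2%.

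A Poisson fit gives more weight to the high early counts. With T from 3 to 10 and q from 0.3 to 0.6 it gives -3.4% to -13.3% for Norway. The model ignores patients ageing out of the 15-29 band. At T = 10 with uniform onset, the pool that began within the band would be about 4.8 rather than 10, so the upper ends are generous.

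**The case against.** Several points on the other side stand.

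- **Start year.** The Norwegian start year is unsettled rather than known to be 2008. The six-year claim fails with either year, but for different cohorts.
- **Earlier records.** Section 7.7 says Danish records reach back to 1978 for admissions and 1995 for outpatient clinics, and 7.6 allows predecessor ICD codes if needed. Look-back beyond the start of a series is possible in Denmark; it is simply not prescribed.
- **Primary analysis.** A reader might infer that a run-in excess produces a spurious vaccine effect in the odds ratio. The documents do not support that. Controls come from the same country, matched on age, calendar year and region (7.1), so a time artefact cannot create an association. Disease that began before vaccination could have prevented it mainly pulls the odds ratio towards 1. In Norway the first targeted cohort was born in 1997 (section 5), so many risk sets from the short cohorts will contain few or no women vaccinated before 17 and carry little weight.
- **Vaccine-era decline.** A reader might also infer that the incidence artefact mimics vaccine impact in all three countries. In Sweden and Denmark most of it falls before 2006. Even in Norway it is steepest in the first few years, before the 1997 cohort reaches 15 in 2012. Rates are also reported for males, who were barely vaccinated; a run-in excess should appear in both sexes, which gives a visible check.

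These points narrow the consequences. They do not reconcile 7.4 with 7.14, make the six-year statement true for Norway, or supply a run-in.

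**Conclusion.** The point holds in this form. Sections 7.4 and 7.14 state different immigrant exclusions. The six-year minimum is untrue for immigrants kept under 7.4 and for native-born Norwegian women in cohorts 1990-1998 (data from 2008) or 1990-1996 (data from 2006). Native-born women in Sweden and Denmark essentially have it.

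For the primary odds ratio the likely effect is dilution, of a size the protocol does not allow one to calculate. That still matters, because 7.8 requires a point estimate of at least 3.0 and expects about 80% power from roughly 60 cases.

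For the incidence series, the direction is clear: early rates too high. In Norway, where the series opens one year before the 2009 programme, a reader could take the fall for vaccine impact. The size rests wholly on assumed durations and contact probabilities; across those tried, the Norwegian artefact is several percent per year. In Sweden and Denmark the effect is on the pre-vaccine baseline and the whole-series trend.

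**What to change.** 1. Put the 7.14 rule into 7.4 for all three countries: exclude everyone who immigrated after age 9, whatever the year.
2. Establish the first year of usable Norwegian diagnosis data and make Table 1 and 7.8 agree with it.
3. Replace the six-year guarantee in 7.14 with the actual look-back by country and birth cohort.
4. For the incidence series, use earlier records as look-back where they exist (Denmark, for example). Otherwise prespecify run-in years for each country and leave them out of the trend test.
5. Add a sensitivity analysis of the primary odds ratio restricted to cases with adequate prior registry coverage, with the required number of years fixed in advance.

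A fixed three-year look-back in the main analysis, which would start Norwegian case accrual in 2011, is not recommended. The three years would be arbitrary, and an unknown number of scarce cases would be lost; a sensitivity analysis answers the same question without that loss.

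The cost is protocol wording, a few immigrant subjects and some early incidence years, mainly in Norway.

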Potential confounders such as highest level of family income and highest level of education achieved by the mother and/or subject income/education (tentatively in tertiles relative to the general age-matched population of the respective countries) will be adjusted for when investigating the primary objective, through inclusion in the conditional logistic regression. Given that most young adult females in their late teens/early 20s in Nordic countries have a similar level of education (i.e., almost all complete high school) and income is often limited due to being in school, adjustment for individual-level income and education will be considered and the decision of which variables to include in the model will depend on association of these variables with RRP outcome, and consideration of collinearity. Additionally, confounder assessment based on G-estimation may be undertaken if considered appropriate following discussion between the Sponsor and investigators.

Sensitivity analyses will be conducted in relation to the primary objective to assess the impact of: vaccine exposure definition (fully vaccinated versus ≥1 vaccine dose), age at

PRODUCT: V501/V503	PROTOCOL/AMENDMENT VERSION NO.: V503-088-01-v1
REVOPS ID NO: NIS009722	CORE DRC APPROVAL DATE: 18JUL2024
EPIDEMIOLOGY NO.(PE STUDIES ONLY): EP08039.017	

vaccination (any age and ≥17 years), applying buffer period between vaccination and disease onset of 6 months (from last dose), outcome definition (ICD-10 code D14.1 only versus cases [of D14.1] that have appropriate topography/morphology or SNOMED/Norpat codes, and cases [of D14.1] with at least one associated treatment/procedural code and/or specified with subcode D14.1.A/"larynx papilloma"), restricted to Gardasil use only (as exposure), and personal history of EGW (yes versus no). OR estimates from the regression model will be inspected in terms of point estimates and precision, for comparison with results from the main analysis. Effect size (OR) estimates are expected to vary across most sensitivity analyses. For example, effectiveness may be higher among females that are fully vaccinated, vaccinated at younger age (prior to sexual debut), without history of EGW, and in analyses including a buffer period and more restrictive outcome definition. For transparency, all preplanned analyses are described here.

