Although **socioeconomic status** appears to be moderately-strongly associated with exposure, there is no evidence suggesting it is associated with outcome. If there is an association with RRP as an outcome, it should be modest in size. However, in the interest of obtaining the best evidence, this association should be evaluated formally, and it is therefore planned to include this factor as a potential confounder in the analysis.

[figure not shown]
Regarding **sexual behavior**, the association with HPV vaccine exposure appears to be weak, whereas that with RRP (outcome) is stronger. This is expected given that causal HPV infection is acquired sexually. In Sweden, riskier sexual behavior was positively associated with willingness to be vaccinated, and therefore bias (due to this confounder) may be expected to be towards the null. Although number of sexual partners cannot explicitly be adjusted for in the proposed register-based study, age of vaccination will be accounted for in the analysis and minimal bias due to sexual behavior would be expected among those vaccinated at younger ages (<17 years), which is defined as exposure in the study primary analysis. Additionally, medical information regarding history of external genital warts (EGW) pre-vaccination may be obtained and used as a proxy for sexual behavior with particular relevance to risk of acquisition of low-risk types of HPV. EGW history is unique as the only STI where individual level register data is validated and available in all countries.

PRODUCT: V501/V503	PROTOCOL/AMENDMENT VERSION NO.: V503-088-01-v1
REVOPS ID NO: NIS009722	CORE DRC APPROVAL DATE: 18JUL2024
EPIDEMIOLOGY NO.(PE STUDIES ONLY): EP08039.017	

Finally, for **smoking habits**, the size of the association and thus potential for confounding due to this factor appears to be modest at most. Nordic registers cannot be used to define individual smoking status as this type of lifestyle factor is not systematically reported to national healthcare registries, especially not among subjects so young (in older age groups, there are proxy codes for smoking-related diagnoses and drugs that could be utilized but these are not relevant here). However, the inclusion of socioeconomic status is expected to serve as at least a partial proxy for smoking behavior, as previously used in HPV vaccine effectiveness studies [20]. It is believed that this approach adequately addresses potential confounding by this factor.

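### Section 7.14 judges confounding by the change in confidence-interval width, which is the wrong quantity, and Section 7.11 selects individual income and education on a basis that 7.14 itself criticises

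*Protocol*

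**What the plan says.** Protocol Section 7.14 describes two routes to the list of confounders: "through subject matter knowledge and literature review, but also (once data on potential confounders are collected) by investigation of variables in the regression model". The test in the second route is whether removing a covariate, with 10% or more given as an example threshold, "alters the width of the confidence interval for the observed (odds ratio) association between exposure and outcome in the actual model". The same sentence contrasts this with forward selection, "which only evaluates association between covariate and outcome" against a p-value threshold, and says "this would not be methodologically correct". Nowhere does the protocol use a change in the exposure OR itself as a criterion.

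Section 7.11 takes a different line for individual-level income and education: "the decision of which variables to include in the model will depend on association of these variables with RRP outcome, and consideration of collinearity". Just before that it says that potential confounders such as family income and mother's education "will be adjusted for when investigating the primary objective, through inclusion in the conditional logistic regression". Annex 1 says of socioeconomic status that "it is therefore planned to include this factor as a potential confounder in the analysis".

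These commitments are loosely worded. Section 7.11 joins the mother's and the subject's own measures as alternatives or additions and calls the tertile coding tentative. Footnote 3 to Table 5 lists education, income, country of birth, and own and maternal genital-wart history only as candidates for the adjusted model.

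**The concern.** A covariate confounds the vaccine estimate when leaving it out moves the estimate. Interval width is a different quantity. On the log scale it depends only on the standard error. On the OR scale it mixes the standard error with the size of the OR. A width rule can therefore drop a covariate that moves the OR, or keep one that does not.

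The two sections also point to different models. Section 7.14 warns against choosing on covariate–outcome association, while 7.11 uses that association, with collinearity, for individual income and education. Two analysts following the protocol could fit different primary models.

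This matters because success is judged against fixed cut-offs: an OR (unvaccinated versus vaccinated) of at least 3.0 and a lower 95% limit of at least 1.33 (Section 7.8). A modest shift from the choice of covariates could move a result across 3.0.

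**Working it through.** The protocol gives no figure to reproduce here, so the check compares the width rule with a 10% change-in-OR rule at the protocol's own planning values.

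**Inputs from the protocol.** 60 cases, 10 controls per case, true OR 3.0, coverage 25% (Section 7.8). Low parental socioeconomic status and vaccine uptake: 0.32 (low education) and 0.53 (low income) in the Swedish subsidised programme; 0.75 to 0.92 for low education in free school-based programmes (Annex 1). These are treated as odds ratios.

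**Assumed inputs.** Covariate prevalence 0.1 to 0.5, covariate–vaccination OR 0.1 to 5, covariate–RRP OR 0.5 to 3. The protocol gives no socioeconomic–AoRRP association.

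**Formulas.** Width on the log scale = 2 × 1.96 × SE. Width on the OR scale = 2 × OR × sinh(1.96 × SE).

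**Step 1: two worked cases** (prevalence 0.33, covariate–RRP OR 2, expected counts).

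| Covariate–vaccination OR | OR (SE) with covariate | OR (SE) without | Change in OR | OR-scale width | Log-scale width |
|---|---|---|---|---|---|
| 0.53 | 3.00 (0.461) | 3.32 (0.458) | +10.6% | 6.19 to 6.79, +9.8% | 0.458/0.461, −0.7% |
| 0.32 | 3.00 (0.477) | 3.56 (0.471) | +18.7% | 6.46 to 7.55, +16.7% | 0.471/0.477, −1.3% |

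In the first row the covariate moves the OR by more than 10% but falls just short on OR-scale width. On the log scale both rows are far from 10%.

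**Step 2: all 96 scenarios** (4 prevalences × 6 covariate–vaccination ORs × 4 covariate–RRP ORs).
- Log scale: the largest change in width is about 5% (0.384/0.406 = 0.946). In the scenario where the OR moves from 3.00 to 5.25 (+75%), the SE goes from 0.581 to 0.553, a change of −4.8%. No covariate reaches 10%.
- OR scale: 3 of 96 scenarios have an OR shift of at least 10% that the width rule misses, and 3 of 96 are flagged although the OR moves by less than 10%.

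**Step 3: simulated matched sets** (60 sets of 11, conditional logistic regression; 30% prevalence, covariate–vaccination OR 0.32, covariate–RRP OR 2). The median OR shift on omission is about +16% and the median log-scale width change about −1%. A 10% change-in-OR rule keeps the covariate in 76% to 78% of data sets across independent runs. OR-scale width keeps it in 69% to 72%, and log-scale width in 0%.

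**Step 4: how large the bias could be.** With a and b the covariate prevalence in vaccinated and unvaccinated women and R the covariate–RRP OR, crude OR / adjusted OR ≈ [1 + (R − 1)b] / [1 + (R − 1)a]. At 30% prevalence and 25% coverage:
- 0.32, R = 2: vaccination 12.3% in the low group and 30.4% in the rest (0.3 × 0.123 + 0.7 × 0.304 = 0.250); a = 0.3 × 0.123/0.25 = 0.147, b = 0.3 × 0.877/0.75 = 0.351; ratio 1.351/1.147 = 1.18. Simulated median about 16%.
- 0.53, R = 1.5: vaccination 17.3% and 28.3%; a = 0.208, b = 0.331; ratio 1.165/1.104 = 1.06. Simulated about 5%.
- 0.75, R = 1.5: vaccination 21.3% and 26.6%; a = 0.256, b = 0.315; ratio 1.157/1.128 = 1.03. Simulated about 2%.

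At the top of that range, a true OR of about 2.6 would be reported as 3.0 (3.0/1.16 = 2.59).

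**Step 5: is change-in-OR a safe replacement?** For a covariate with 30% prevalence that predicts RRP but is unrelated to vaccination, the change-in-OR rule still flags it in about 12% to 13% of data sets at RRP OR 3 (OR-scale width: 16%) and 32% to 34% at RRP OR 5 (width: 41% to 42%). With about 60 cases, either data-driven rule reacts to noise.

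**The case against.** The strongest defence is that the main socioeconomic confounders do not depend on the rule. Section 7.11 plans adjustment for family income and mother's education, and Annex 1 plans to include socioeconomic status. The 0.32 figure is for parental education, so the 16% shift describes omitting something the protocol intends to include. This largely stands. It leaves exposed individual income and education, country of birth, and genital-wart history, and the commitment on the parental variables remains hedged.

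Second, Section 7.14 speaks of the interval for the odds ratio and Table 5 reports ORs with intervals, so the OR scale is the natural reading. There the width rule nearly tracks a change-in-OR rule. A reader might infer that neither section's rule can detect confounding; on the OR scale that goes too far. The protocol names no scale, however, and the result turns on it.

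Third, the width check is permissive, beside an a priori route. Section 7.14 objects to forward selection on outcome association alone with a p-value threshold; 7.11 states no threshold and adds collinearity. The sections are unharmonised rather than flatly opposed.

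Fourth, a reader might infer that the outcome-association rule has almost no power because few vaccinated cases are expected. That is wrong. Power to detect a covariate–outcome association depends on all 60 cases and on covariate prevalence. In the Step 3 scenario it is about 68% to 69% after adjustment for vaccination.

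Finally, Annex 1 finds no evidence that socioeconomic status is associated with the outcome and expects any association to be modest. It also raises greater care-seeking at higher status, which would reverse the direction of bias.

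**Conclusion.** The width criterion in Section 7.14 is stated wrongly. On the log scale it would retain essentially no confounder; on the OR scale it approximates a change-in-OR check, with disagreements near the threshold. Section 7.11 adds a separate criterion for individual income and education on a basis that 7.14 criticises. Together they leave the primary adjustment set open.

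The likely effect is limited. The exposed covariates are mainly individual income and education, country of birth, and own and maternal genital-wart history. The illustrated OR shift of about 2% to 16% rests on assumed socioeconomic–RRP ORs of 1.5 to 2 and 30% prevalence. Its upper end combines the most extreme uptake figure in Annex 1 with an assumed RRP OR of 2, and its direction would reverse if low status went with fewer diagnoses. No size was estimated for country of birth or genital-wart history. A reader might infer that the planned analysis is biased by about 15% in favour of the vaccine; the documents do not support that, because adjustment for family income and mother's education is planned. This is a correction worth making before the primary model is fitted, and it does not invalidate the design.

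**What to change.** - Prespecify one adjustment set for the primary model from Annex 1, with mother's education and family income in unconditionally. State for each of individual income, individual education, country of birth, and own and maternal genital-wart history whether it is in or out.
- Delete the interval-width criterion from Section 7.14 and the outcome-association criterion from Section 7.11. Align footnote 3 of Table 5 with the fixed set.
- If an empirical check is kept, report the change in the exposure OR as a sensitivity analysis only. It should not decide the primary model, given the false flags in Step 5.
- Do not let any such check bring in genital-wart history. Section 7.6.3 warns that adjusting for it may absorb part of the vaccine effect.

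The cost is a few sentences in 7.11 and 7.14 and one footnote. The model gains a few parameters, so intervals become slightly wider.
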